3.7 Nonclinical Study Data

(1) Toxicity study

In nonclinical studies, the safety of Engensis (VM202) was assessed with an intramuscular single-dose toxicity study in rats as well as an intravenous single-dose toxicity study. Additionally, safety was also assessed in intermittent intramuscular repeat-dose toxicity studies (weekly or monthly) in rabbits and rats used.

The possibility of genomic integration at the injection site or the possibility of distribution and persistence of Engensis (VM202) in reproductive tissues were evaluated in experiments conducted in rats. In the intramuscular administration of mice, the possibility of Engensis (VM202) to induce humoral immune response was evaluated through an experiment that either administered or did not administer an adjuvant concomitantly.

In conclusion, the results of various toxicity studies showed that Engensis (VM202) was well-tolerated in all studies, and the only toxicity was mild and transient injection site irritation. Evidence of systemic toxicity was not shown at all in any of the studies, and there was also no evidence of human HGF detected in the serum of rats or rabbits after intramuscular injections. [lower limit of quantitation (LLOQ) = 125 pg/mL]. Genomic integration, germ cell transmission, immunostimulatory effects, etc., were not shown at all when Engensis (VM202) was administered intramuscularly.

[figure not shown]

Figure 6 Toxicity study data (see IB)

(2) Efficacy study

After administering Engensis, the following efficacy assessments were performed.

- Nerve regeneration effects: After administering Engensis (VM202), the reconstruction of myelin sheath by Schwann cells was promoted, and regeneration of the degenerated axon was promoted as well.
- Muscle regeneration effects: After administering Engensis (VM202), nerve damage-induced amyotrophy was improved. The muscle regeneration process after muscle

damage was promoted.

- Pain reduction effects: After administering Engensis (VM202), neuropathic pain was reduced.
- Cardiovascular function improvement effects: After administering Engensis (VM202), blood flow was improved as angiogenesis was promoted, and cardiac function was improved as well.

[figure not shown]
Thus, these study results for efficacy and safety from nonclinical studies provide a sufficient rationale for conducting an Engensis (VM202) clinical study in CMT patients.

[figure not shown]

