- 20) Individuals who have shown significant adverse events such as hypersensitivity reactions to the investigational product
- 21) Pregnant or breastfeeding females
- 22) Other individuals determined ineligible by the principal investigator to participate in the clinical study due to other reasons including clinical laboratory test results

5.3.4 **Assignment of Subject Numbers**

Subjects that will be voluntarily participating in this clinical study shall be assigned screening numbers (completion of informed consent form - checking eligibility with inclusion/exclusion criteria), and shall be assigned allocation numbers if they satisfy the inclusion/exclusion criteria.

PRT NO: VMCMT-001 Confidential 2021.06.07 Version :4.0 52 / 53

A screening number shall start with the letter "S" and consist of a five-digit number, and it shall be assigned base on the order of the subjects' written consent at the institution.

For example, the meaning of "S01001" is as follows:

Allocation numbers shall be assigned, in the order of enrollment in the clinical study, to the subjects who have satisfied the inclusion/exclusion criteria after completing all screening tests. The allocation number shall start with the letter "A" followed by a five-digit number.

For example, the meaning of "A01001" is as follows:

A	01	001
Allocation number (Acronym of allocation)	Institution (Indicated as "01" since it is a single center)	Allocation number

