^{**} IP administration: Administration shall be performed after proceeding with all pre-administration assessment items.

- 1) Subject background survey: A survey shall be performed on demographic information and history of alcohol and tobacco use, etc.
- 2) Medical history survey: A survey shall be performed on medical history within 6 months before Visit 1 (screening). However, medical history/treatment history related to cancer shall be surveyed regardless of the time period. Clinically significant medical conditions or abnormalities observed during the period from the obtainment of the informed consent form until the administration of the investigational product shall be deemed as medical history. It shall be surveyed whether the national cancer screening (gastric cancer, colon cancer, liver cancer, lung cancer, cervical cancer, breast cancer) examinations relevant to the patient's age are taken and the results are within the normal range. In case of cervical cancer, if it cannot be confirmed that the national cancer screening examinations were taken within 2 years and the results are within the normal range, an examination and a pap smear shall be performed at the institution to verify normal range results.
- 3) Physical examination: Information shall be collected for examination items consisting of external appearance, skin, head/neck, chest/lungs, heart, abdomen, urinary/reproductive system, limbs, musculoskeletal system, nervous system, lymph nodes, and other items.
- 4) Body measurement (weight measurement): Height, weight, and BMI shall be measured. Height and BMI shall be measured only at screening (Visit 1).
- 5) Virus serology test: HIV, HBsAg, Anti-HBs, Anti-HCV
- Complete blood cell count and general blood chemistry tests: The laboratory test items are as follows:
 - Complete blood cell count: WBC, RBC, Hb, Hct, MCV, MCH, MCHC, PLT, ESR, MPV, differential count of WBC (Band neutrophil, Segmented neutrophil, Eosinophil, Basophil, Lymphocyte, Monocyte)
 - General blood chemistry test: total protein, albumin, globulin, A/G ratio, cholesterol, total bilirubin, AST, ALT, fasting glucose, BUN, creatinine, estimated GFR, Ca²⁺, phosphate, Na⁺, K⁺, Cl⁻, CRP, triglyceride, HDL-cholesterol, LDL-cholesterol

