At Visit 1, female subjects of childbearing potential shall undergo a urine pregnancy test (urine β -HCG, beta-human chorionic gonadotropin). At Visit 1 (screening), urine pregnancy tests shall be performed in females of childbearing potential (from post-menarche females to females \geq 50 years of age within 1 year of menopause, or from post-menarche females to females < 50 years of age within 2 years of menopause). A serum pregnancy test may serve as a substitute if collection of urine fails. However, patients with surgical menopause (hysterectomy, bilateral oophorectomy, etc.) or who underwent sterilization surgery (bilateral tubal ligation, bilateral tubectomy) may be excluded. Menopause refers to the state after 1 year of amenorrhea. The test result must be negative, and effective methods of contraception shall be documented. The samples shall be immediately discarded when the test is completed. Acceptable methods of contraception are as follows:

- · Drug: Oral contraceptives, skin patches, or progestin formulations (implants or injections)
- · Barrier method: Condoms, diaphragms, intrauterine devices (IUDs), vaginal suppositories
- Abstinence: Complete abstinence (However, periodic abstinence (e.g., calendar method, ovulation method, and sympto-thermal method) and self-restraint are not considered as acceptable methods of contraception.)

Electrocardiogram

A 12-lead electrocardiogram shall be performed at Visit 1 (screening). If there are results from a test performed at the same institution within 4 weeks before Visit 1 (screening), they may serve as a substitute.

Vital signs

Vital signs including blood pressure (measurement shall be taken with the subject in a sitting position after resting for at least 10 minutes prior to measurement), temperature, heart rate per minute, and respiratory rate per minute shall be measured. The measurement results shall be recorded in the subjects' case report forms. This shall be performed at Visit 1 (screening) and throughout the clinical study every time a subject makes a visit (on the drug administration days consisting of Visits 2, 3, 4, and 5, it shall be performed both prior to administration and 2 ± 1 hours after administration). However, if there is a subject with abnormal findings in the test at Visit 3 (Day 14), a follow-up test may be performed at Day 30 depending on the decision of the principal investigator.

Concomitant medications survey

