6.1.2 Visit 2 (Administration 1, Day 0)

6.1.2.1 Before Administration of Investigational Product

The following shall be performed prior to administering the investigational product.

Hospitalization (if applicable)

Subjects shall be hospitalized on the day before administration of the investigational product and their vital signs shall be measured. If they are not hospitalized, vital signs may be omitted, and the hospitalization day in the case report form shall be recorded the same as the test day prior to administration.

· Final confirmation of inclusion/exclusion criteria

Assignment of allocation numbers* when inclusion/exclusion criteria are satisfied
 *: See section 5.3.4 Assignment of Subject Numbers

Body measurement (weight measurement)

A subject's weight shall be measured at Visit 1 and throughout the clinical study every time a subject makes a visit (shall be performed prior to administering the investigational product at Visits 2, 3, 4, and 5).

Complete blood cell count

This shall be performed at Visit 1 and throughout the clinical study every time a subject makes a visit (shall be performed prior to administering the investigational product at Visits 2, 3, 4, and 5). However, if there is a subject with abnormal findings in the test at Visit 3 (Day 14), a complete blood cell count and a general blood chemistry test may be performed at Day 30 depending on the decision of the principal investigator. The complete blood cell count items are as follows:

WBC, RBC, Hb, Hct, MCV, MCH, MCHC, PLT, ESR, MPV, differential count of WBC (Band neutrophil, Segmented neutrophil, Basophil, Lymphocyte, Monocyte)

General blood chemistry test

This shall be performed at Visit 1 and throughout the clinical study every time a subject makes a visit (shall be performed prior to administering the investigational product at Visits 2, 3, 4, and 5). However, if there is a subject with abnormal findings in the test at Visit 3 (Day 14), a complete blood cell count and a general blood chemistry test may be performed at Day 30 depending on the decision of the principal investigator. Since a blood glucose test is included, the subject shall maintain an 8-hour fasting state prior to the test. The general blood chemistry test items are as follows:

total protein, albumin, globulin, A/G ratio, cholesterol, total bilirubin, AST, ALT, fasting glucose, BUN, creatinine, estimated GFR, Ca²⁺, phosphate, Na⁺, K⁺, Cl⁻, CRP, triglyceride, HDL-cholesterol, LDL-cholesterol

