This shall be performed at Visit 1 and throughout the clinical study every time a subject makes a visit (shall be performed prior to administering the investigational product at Visits 2, 3, 4, and 5). However, if there is a subject with abnormal findings in the test at Visit 3 (Day 14), urinalysis may be performed at Day 30 depending on the decision of the principal investigator.

The urinalysis items are as follows:

Color, turbidity, specific gravity, pH, albumin, glucose, ketones, bilirubin, blood, urobilinogen, nitrite, leukocyte esterase, microscopy (RBC, WBC, casts)

Vital signs

Vital signs including blood pressure (measurement shall be taken with the subject in a sitting position after resting for at least 10 minutes prior to measurement), temperature, heart rate per minute, and respiratory rate per minute shall be measured. The measurement results shall be recorded in the subjects' case report forms. This shall be performed at Visit 1 (screening) and throughout the clinical study every time a subject makes a visit (on the drug

administration days consisting of Visits 2, 3, 4, and 5, it shall be performed both prior to administration and 2 ± 1 hours after administration). However, if there is a subject with abnormal findings in the test at Visit 3 (Day 14), a follow-up test may be performed at Day 30 depending on the decision of the principal investigator.

Concomitant medications survey

The brand names and ingredient names of concomitant medications shall be surveyed at every visit and recorded in the case report form. All medications and treatments administered within 6 months before Visit 1 (screening) shall be surveyed. Previous medications and previous treatments shall be defined as all previously collected medications and treatments before Visit 2 (first administration of investigational product). Concomitant medications and treatments shall refer to all medications that have been administered at least once starting from Visit 2 (first administration of investigational product) and throughout the clinical study. The categories of collected medications and treatments shall follow this definition. The following shall also be surveyed for each medication:

- Brand name
- Indications for medication administration (reason for administration)
- Dose/strength, administration route, number of administrations
- Start and discontinuation dates of administration (whether to continue when the clinical study is terminated)

FDS

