7.3 Precautions

VM202 must not be used on subjects with severe infection. Women of childbearing potential who are administered with VM202 must be careful to avoid pregnancy.

	than for any other reason; The AE disappears when administration of the investigational product is suspended.
Possibly related	 There is evidence that the investigational product has been administered and the time sequence of the AE onset is reasonable; The AE is caused by the investigational product at the same level as other probable reasons; The AE disappears when administration of the investigational product is suspended (if performed);
Unlikely	 There is evidence that the investigational product has been administered; There are other causes with higher possibility than the investigational product; The administration suspension (if performed) result is negative or ambiguous; The re-administration (if performed) result is negative or ambiguous;
Not related	 The subject has not been administered with the investigational product; The time sequence of the administration and the AE onset is not reasonable; There are other obvious causes for the AE;
Unassessable	 There is insufficient evidence to determine the relationship; Information is insufficient or conflicting to determine, and cannot be supplemented or verified;

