7.4.7 Pregnancy report

Female subjects of childbearing potential and male subjects who are sexually active with women of childbearing potential must practice appropriate contraception until the 7th visit (last visit, Day 270) after the last administration of the investigational product.

The appropriate contraception methods acknowledged in this clinical study are:

- Hormonal contraceptives
- Insertion of an Intrauterine device or system
- Double barrier method*(spermicide and condom with vaginal diaphragm, vaginal sponge, or cervical cap)
 - * Both male (condom) and female (vaginal diaphragm, vaginal sponge or cervical cap) must use contraceptive devices together with spermicide.
- Sterilization surgery (vasectomy, bilateral tubal ligation, etc.)
- Complete abstinence: If preferred by the subject and matched with everyday lifestyle. [Periodic abstinence and coitus interruptus are not acknowledged as contraception.]

The Sponsor has the obligation to follow up on the results of pregnancy reported by female and male subjects during the clinical study. If it is not suspected that the investigational product interfered with the efficacy of appropriate contraception and contraceptives, the pregnancy itself is not considered an AE. In addition, voluntary induced abortion without complications, other than therapeutic abortion, is not considered an AE.

Within 24 hours of becoming aware of pregnancy, the Investigator shall prepare an initial pregnancy report and report it to the Sponsor. The Investigator shall track and document the process and results of all pregnancies even if the subject withdraws consent or terminates the clinical study. In addition, the investigator shall prepare a pregnancy result report and report it to the Sponsor within 24 hours of becoming aware of the results of any pregnancy (e.g., spontaneous labor, spontaneous abortion, etc.).

All SAEs (e.g., severe maternal complications, premature birth, therapeutic abortion, ectopic pregnancy, stillbirth, neonatal death, congenital anomaly, birth defects, etc.) that occurred from beginning of pregnancy to four weeks after childbirth shall be recorded in the SAE report and must be reported immediately to the PVA of DT&SanoMedics Co., Ltd., following the procedure in 7.4 Adverse Events.

8 Statistical Method

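### The only scheduled pregnancy test is at screening, so inside the visit windows the latest negative result can be 127 days old at dose 3 and 141 days old at dose 4

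*Protocol*

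**What the plan says.** Section 6.1.1 of the protocol places the test at screening: "At Visit 1, female subjects of childbearing potential shall undergo a urine pregnancy test". Serum may be used if urine cannot be collected. Both schedule tables (Synopsis and Section 6.1), their footnote 10 and inclusion criterion 7 agree that the test belongs to screening.

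At Visit 2, before dose 1, Section 6.1.2.1 calls for "Final confirmation of inclusion/exclusion criteria" but lists no new pregnancy test. The pre-dose lists for doses 2, 3 and 4 (Sections 6.1.3.1, 6.1.5.1 and 6.1.6.1) contain neither a pregnancy test nor a re-check of eligibility.

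Several rules show that the protocol does not want a pregnant woman to be dosed:

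- Exclusion criterion 21 (Section 5.3.3) is "Pregnant or breastfeeding females".
- Section 7.3 states: "Women of childbearing potential who are administered with VM202 must be careful to avoid pregnancy".
- Section 7.4.7 says that women of childbearing potential, and men sexually active with such women, "must practice appropriate contraception until the 7th visit (last visit, Day 270) after the last administration of the investigational product".
- Section 5.5.3(2), item 3, permanently stops dosing when violations of the entry criteria come to light during the study.

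Section 7.4.7 also requires a pregnancy to be reported to the sponsor within 24 hours of the investigator learning of it.

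**The concern.** Dosing runs to about Day 104, with a pause of roughly eleven weeks between doses 2 and 3. A single test before dose 1 says nothing about a conception after screening. A woman whose contraception fails, and who has not noticed the pregnancy, would receive the next 14 mg. If this happened in the pause, she could receive both remaining doses (2 x 14 = 28 mg of the 56 mg total).

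The existing controls reduce the chance of pregnancy or act once it is known. They do not detect it. Contraception is documented at screening, and no later visit list re-checks it. The stopping rule and the reporting rule both depend on somebody already knowing. Adverse-event questioning is not aimed at pregnancy either, because Section 7.4.7 does not ordinarily count a pregnancy as an adverse event.

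**Working it through.** The plan states no figure for the age of the test result, so there is none to reproduce. The check is calendar arithmetic.

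**Inputs (protocol Sections 6.1.1 to 6.1.6).** Screening: Day -30 to Day -1. Dose 1: Day 0. Dose 2: Day 14 ± 5, so Day 9-19. Dose 3: Day 90 ± 7, so Day 83-97. Dose 4: Day 104 ± 7, so Day 97-111.

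**Age of the latest negative result.** Minimum = earliest dosing day + 1. Maximum = latest dosing day + 30.

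| Dose | Minimum (days) | Maximum (days) |
|---|---|---|
| 1 | 0 + 1 = 1 | 0 + 30 = 30 |
| 2 | 9 + 1 = 10 | 19 + 30 = 49 |
| 3 | 83 + 1 = 84 | 97 + 30 = 127 |
| 4 | 97 + 1 = 98 | 111 + 30 = 141 |

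With screening on Day -30 and doses on their nominal days, the ages are 30, 44, 120 and 134 days.

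These limits hold only inside the visit windows. Section 5.7.2 requires a 14-day quarantine for COVID-19 cases and close contacts. It suspends subjects who have not recovered by their next visit and resumes the visit procedures afterwards. A dose can therefore fall later, and the result can then be older.

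**Where a repeat test gains most.** The gap from dose 2 to dose 3 is 83 - 19 = 64 to 97 - 9 = 88 days. Dose 2 follows dose 1 by 9-19 days, and dose 4 follows dose 3 by at most 111 - 83 = 28 days. A test at Visit 4 alone makes the result same-day at dose 3 and at most 28 days old in-window at dose 4, instead of 141.

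**How many pregnancies (illustration only).** The documents give neither the number of women of childbearing potential nor a pregnancy rate on contraception, so both are assumed. Expected number = women x rate per woman-year x days / 365.

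| Assumed women | Assumed rate per 100 woman-years | Over 141 days (factor 0.386) | Over 88 days (factor 0.241) |
|---|---|---|---|
| 3 | 1 | 0.01 | 0.01 |
| 6 | 5 | 0.12 | 0.07 |
| 12 | 10 | 0.46 | 0.29 |

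The last row is extreme, since both sexes aged 19 to 65 are eligible. The figures are not bounds. They count some pregnancies that the woman would recognise and report, and some too early for urine HCG. Against that, they ignore delays outside the windows, and one unrecognised pregnancy could receive more than one dose.

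**The case against.** **Screening-only testing is a consistent design choice.** The tables, footnote, criterion and procedure text agree, so no protocol rule is broken. That stands, and the point is therefore an improvement, not an error.

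**Controls exist.** Inclusion criterion 8 requires contraception throughout the study, and item 3 of Section 5.5.3(2) arguably already stops dosing if a lapse or a pregnancy is found. That also stands, but both act on discovery and neither looks for a pregnancy. The contraception standard itself varies: Section 5.3.2 accepts condoms as a barrier method, whereas Section 7.4.7 asks for double barriers with spermicide.

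**The event is rare and harm is unproven.** A reader might infer that the plan exposes fetuses to a known hazard. The documents do not support that. Section 3.6 describes expression as local. Section 3.7 reports no human HGF detected in the serum of rats or rabbits and states: "Genomic integration, germ cell transmission, immunostimulatory effects, etc., were not shown at all when Engensis (VM202) was administered intramuscularly". No embryo-fetal data are visible, but some toxicity tables and figures are not shown here and the text points to the Investigator's Brochure, so this is not evidence that such data are lacking. A reader might also take 0.46 as a worst case. It is not one, because its inputs are assumed and delays can lengthen the period.

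**The change may come late.** Section 5.7.1 says enrolment was complete at version 4.0, and allocation numbers are given at Visit 2 before dose 1, so a Visit 2 test probably has no subject left to apply to. SAP Section 3.3 describes assessments to Day 270 largely in the past tense, which suggests, without proving, that dosing was finished or well advanced. Section 16 reserves amendments after study start for exceptional cases. All this narrows the fix to doses still to be given.

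**Four tests may be more than needed.** Doses 2 and 4 follow closely on doses 1 and 3. This supports putting Visit 4 first.

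**Conclusion.** The point holds as a cheap improvement. The only scheduled test is at screening, and nothing scheduled would find an unrecognised pregnancy before doses 2 to 4. At dose 1 the result is at most 30 days old. At doses 3 and 4 it is at least 84 and 98 days old even with the latest screening and earliest dosing, and up to 127 and 141 days old in-window.

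These ages follow from the protocol's windows alone. Any count of pregnancies rests on assumed numbers of women and assumed rates. It is small in 12 subjects, and the documents do not allow the consequence to be sized in either direction. The case rests on the protocol's own exclusion and precaution, set against the low cost of the check. It does not show that a pregnant woman was dosed or that the product harms a fetus.

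**What to change.** In both schedule tables, footnote 10 and the pre-dose sections, add for females of childbearing potential: urine beta-HCG (serum if urine collection fails) before administration, with injection only after a negative result has been read. Apply it at every dosing visit still to be given. If only one test can be added, make it Visit 4. Visit 2 needs it only if some subject has not yet had dose 1, which is unlikely.

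No new visit or urine collection is needed. Urinalysis already "shall be performed prior to administering the investigational product at Visits 2, 3, 4, and 5". Use a separate portion of that urine, because Section 6.1.1 has pregnancy-test samples discarded at once. The schedule note in Section 6.1 already secures the order once the test is listed: "Administration shall be performed after proceeding with all pre-administration assessment items".

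The number of tests is at most 12 x 4 = 48. It is 36 if everyone has had dose 1, 24 if only doses 3 and 4 remain, and 12 for Visit 4 alone. It will be lower in practice, since only women of childbearing potential are tested.

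The main cost is a signed amendment with regulatory or ethics approval, an eCRF update and possibly a revised consent form. The other downsides are a short wait on dosing days and very early pregnancies that a same-day negative would still miss.
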